Appendix II – Response Criteria for MDS⁴⁷

Table 3. Proposed modified International Working Group response criteria for altering natural history of MDS⁷

Category	Response criteria (responses must last at least 4 wk)
Complete remission	
Bone marrow: $\leq 5\%$ myeloblasts with normal maturation of all cell lines*
 
Persistent dysplasia will be noted*†
 
Peripheral blood‡
 
Hgb ≥ 11 g/dL
 
Platelets $\geq 100 \times 10^9/L$
 
Neutrophils $\geq 1.0 \times 10^9/L$†
 
Blasts 0%

Partial remission	
All CR criteria if abnormal before treatment except:
 
Bone marrow blasts decreased by $\geq 50\%$ over pretreatment but still $> 5\%$
 
Cellularity and morphology not relevant

Marrow CR†	
Bone marrow: $\leq 5\%$ myeloblasts and decrease by $\geq 50\%$ over pretreatment†
 
Peripheral blood: if HI responses, they will be noted in addition to marrow CR†

Stable disease	Failure to achieve at least PR, but no evidence of progression for > 8 wks
Failure	Death during treatment or disease progression characterized by worsening of cytopenias, increase in percentage of bone marrow blasts, or progression to a more advanced MDS FAB subtype than pretreatment
Relapse after CR or PR	
At least 1 of the following:
 
Return to pretreatment bone marrow blast percentage
 
Decrement of $\geq 50\%$ from maximum remission/response levels in granulocytes or platelets
 
Reduction in Hgb concentration by ≥ 1.5 g/dL or transfusion dependence

Cytogenetic response	
Complete
 
Disappearance of the chromosomal abnormality without appearance of new ones
 
Partial
 
At least 50% reduction of the chromosomal abnormality

Disease progression	
For patients with:
 
Less than 5% blasts: $\geq 50\%$ increase in blasts to $> 5\%$ blasts
 
5%-10% blasts: $\geq 50\%$ increase to $> 10\%$ blasts
 
10%-20% blasts: $\geq 50\%$ increase to $> 20\%$ blasts
 
20%-30% blasts: $\geq 50\%$ increase to $> 30\%$ blasts
 
Any of the following:
 
At least 50% decrement from maximum remission/response in granulocytes or platelets
 
Reduction in Hgb by ≥ 2 g/dL
 
Transfusion dependence

Survival	
Endpoints:
 
Overall: death from any cause
 
Event free: failure or death from any cause
 
PFS: disease progression or death from MDS
 
DFS: time to relapse
 
Cause-specific death: death related to MDS

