5.1. Inclusion Criteria

- 5.1.1 Diagnosis of O-AML that is refractory to or intolerant to standard therapy and is no longer likely to respond to such therapy (at least one line of therapy); or
Diagnosis of MDS/CMML that is refractory to or intolerant to standard therapy and is no longer likely to respond to such therapy (at least one line of therapy)
- 5.1.2 Confirmed histologic diagnosis on bone marrow biopsy and aspirate within 28 days of trial entry prior to starting cycle 1.
- 5.1.3 Platelets $> 10 \times 10^9/L$
- 5.1.4 Age ≥ 18 years
- 5.1.5 ECOG performance status of 0, 1 or 2 (appendix III).
- 5.1.6 Prior systemic chemotherapy, immunotherapy, or biological therapy, radiation therapy and/or surgery are allowed; prior use of systemic methotrexate > 1 month prior to study entry is allowed. Intrathecal methotrexate is allowed prior to and during treatment per investigator discretion.

Time since prior therapy and the first dose of study drug:

- 5.1.7 At least 2 weeks since prior radiation, non cytotoxic small molecule drugs, prior major surgery (defined as a surgery involving a risk to the life of the patient; specifically: an operation upon an organ within the cranium, chest, abdomen, or pelvic cavity), prior systemic FDA-approved therapy
- 5.1.7 Patient must have recovered from the acute toxic effects (\leq grade 1 CTCAE v.4.0) of previous anti-cancer treatment prior to study enrollment; the only exception is that grade 2 neuropathy is permitted

- 5.1.8 Adequate organ function within 14 days of study registration defined as:

System	Laboratory Values
Hematologic	
Platelets	$> 10 \times 10^9/L$
Hepatic	
Bilirubin total	$\leq 1.5 \times ULN$
Alkaline Phosphatase, AST and ALT	$\leq 3 \times ULN$ ($< 5 \times ULN$ is acceptable if liver has tumor involvement)
Renal	
Serum Creatinine, or Creatinine Clearance, or GFR, or 24 hour urine creatinine clearance	$\leq 1.5 \times ULN$ $\geq 60 \text{ mL/min}$ $\geq 60 \text{ mL/min}$ $> 50 \text{ mL/min}$

- 5.1.9 Negative serum pregnancy test in females. Male and female patients with reproductive potential must use an approved contraceptive method if appropriate (for example, abstinence, oral contraceptives, implantable hormonal contraceptives, or double barrier methods) during, and for 3 months after the last dose of 765IGF-MTX.

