8.1. Standard of Care Procedures

	Baseline, within 28 days of enrollment	Each treatment cycle ^a			Every 8 weeks (± 1 week)	30 days (± 1 week) after final dose of 765IGF-MTX ¹
		Day 1 ² (±1 day)	Day 8 (±1 day)	Day 15 (±1 day)		
Signed consent (Registration/ Enrollment must occur within 30 days.)	X					
Medical history	X	X				X
Review of prior therapy	X					
Bone marrow biopsy and aspirate confirming disease and blast count ³	X				X ³	
Physical exam	X	X				X
Vital signs	X	X	X	X		X
Height, weight	X	X				X
Concomitant meds review	X	X	X	X		X
Performance status	X	X				X
Symptom and toxicity	X	X	X	X		X ³
CBC w/ diff	X	X	X	X		X
CMP (with: calcium, glucose, sodium, potassium, CO ₂ , chloride, BUN, creatinine, albumin, ALT, AST, bilirubin, alkaline phosphatase, total protein)	X	X	X	X		X
Uric acid (cycle 1 only)	X	X		X		
LDH	X	X				
HbA1C for diabetic patients	X					X
Serum pregnancy test for females of child- bearing potential	X					
ECG ⁴	X	X				X
765IGF-MTX administration			X	X		

^a Subsequent cycles beyond cycle 1 must meet the criteria found in section 7.3 and may begin 1 day earlier or up to 2 days later to accommodate scheduling issues.

¹ For patients who leave treatment with a response, repeat appropriate disease assessment every 6-12 weeks until progression or start of a new treatment.

² For cycle 1 only, tests and procedures do not need to be repeated if done within 3 days of day 1.

³ Bone marrow biopsy should be at end of end of cycle 2, and every 2 cycles thereafter to cycle 6. Patients who achieve response (CR) could have repeat bone marrow biopsies per MD discretion.

⁴ ECG performed at screening, at cycle 1 and at the end of study visit 30 days after the final dose.

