13.2.1. Efficacy Endpoints

The numbers of overall complete remissions (patients with a best objective response of CR or CRi), and overall remissions (patients with a best objective response of CR, CRi or PR) will be summarized by observed rates and estimated 95% CIs. If there are sufficient numbers of patients achieving remissions for an analysis to be informative, logistic regression will be used to model the probability of achieving a remission as a function of the assigned 765IGF-MTX dose level for Cycle 1. Other factors may be added to the model to investigate their prognostic value in predicting remission.

In general, missing values will not be replaced by imputed values. Patients who, for any reason, do not supply bone marrow for response assessment are counted among those not achieving a response.

Kaplan-Meier time-to-event analyses will be conducted on overall survival and progression-free survival. Mortality (all causes) at certain landmark time points (e.g., 90 and 180 days) will also be estimated together with 95% CIs. Cox proportional hazards models will be fit to these time-to-event endpoints with the assigned 765IGF-MTX dose level for Cycle 1 serving as the independent variable in the model.

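### Marrow CR has no minimum starting blast level, so an MDS patient who enters at 5% blasts or less can be counted as a remission on a halving that lies within counting error

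*Combined protocol and SAP*

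**What the plan says.** Appendix II requires two things for marrow CR: at most 5% myeloblasts, and, in its words, "myeloblasts and decrease by $\geq 50\%$ over pretreatment". It sets no starting level and no blood-count criterion. The column heading adds a duration: "Response criteria (responses must last at least 4 wk".

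Entry for this group is "Diagnosis of MDS/CMML that is refractory to or intolerant to standard therapy and is no longer likely to respond to such therapy" (5.1.1), with "Confirmed histologic diagnosis on bone marrow biopsy and aspirate within 28 days of trial entry prior to starting cycle 1" (5.1.2). Neither item, nor section 5.2, mentions a blast threshold. The baseline procedure in 8.1 is "Bone marrow biopsy and aspirate confirming disease and blast count", so the count is recorded but no cut-off is attached to it.

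Section 3.2.2 and the abbreviation list equate CRi with marrow CR. Section 13.2.1 then defines overall complete remissions as "patients with a best objective response of CR or CRi", and overall remissions add PR.

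Marrows are scheduled at the end of cycles 2, 4 and 6. Footnote 3 of 8.1 adds: "Patients who achieve response (CR) could have repeat bone marrow biopsies per MD discretion". Footnote 4 of 8.2 nevertheless keeps research marrows after cycles 2, 4 and 6.

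**The concern.** A patient who enters at 2% blasts meets the absolute part of the rule before the first dose. The only remaining condition is relative, and a reading of 1% satisfies it.

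Other rows of the same table do not work this way. Progression for a patient under 5% needs both a relative rise of at least half and a crossing above 5%. PR needs blasts still above 5%. Only marrow CR lets a low-blast patient qualify on relative change alone.

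The 4-week duration could limit this, but marrows are 8 weeks apart, no confirming marrow is required, and marrow CR has no blood component that interim counts could confirm.

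At stake are the complete remission rate and ORR. Dose levels hold 1 to 9 patients and 13.4.2 reports response by dose and disease, so one false event in 9 reads as 11% (exact 95% CI 0.3 to 48%). RFS and CIR would also be touched if the Appendix I outcome definitions, which start from CR or CRi, are applied to MDS. A blast count that drifts back to its starting level could then be read as a relapse.

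**Working it through.** The plan states no figure on this point, so there is none to reproduce. The check asks how often a patient whose blasts do not change would meet the marrow CR numbers.

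**Inputs from the plan:** at most 5% blasts and at least a 50% fall (Appendix II); three scheduled follow-up marrows (8.1); no entry minimum (5.1).

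**Assumption:** *n* = 200 or 500 cells counted, which the documents do not give. Only counting error is modelled; variation between samples or readers would normally add to it.

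**Model:** the true blast fraction *p* is constant, and baseline count X0 and each follow-up count X are independent Binomial(*n*, *p*). For a given baseline x0, the chance of qualifying on one marrow is q = P(X ≤ min(⌊x0/2⌋, 0.05*n*)). Then:

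- best of three marrows: 1 − (1 − q)³
- two consecutive marrows among three: 2q² − q³

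Each is averaged over x0.

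**One case by hand:** *n* = 200, *p* = 2%, baseline observed at exactly 4 cells. q = P(X ≤ 2) = 0.235. Best of three is 1 − 0.765³ = 0.55. Two consecutive is 2(0.235²) − 0.235³ = 0.098.

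**Averaged over observed baselines above 0 and at most 5%:**

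| True blasts | 1% | 2% | 3% | 4% |
|---|---|---|---|---|
| 200 cells, one marrow | 37% | 22% | 14% | 7% |
| 200 cells, best of three | 68% | 47% | 33% | 19% |
| 200 cells, two consecutive | 25% | 12% | 5% | 1% |
| 500 cells, one marrow | 18% | 8% | 4% | 1% |
| 500 cells, best of three | 41% | 21% | 10% | 3% |
| 500 cells, two consecutive | 9% | 3% | 0.7% | <0.1% |

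**Effect of possible remedies** (200 cells, three marrows, per patient at each true level whatever baseline is observed, provided it is above zero):

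| True blasts | 1% | 2% | 3% | 4% |
|---|---|---|---|---|
| Best of three, no floor | 59% | 47% | 35% | 26% |
| Confirmation only | 22% | 12% | 7% | 4% |
| Floor only (observed baseline above 5%) | 0.0% | 0.3% | 3.5% | 11.1% |
| Floor and confirmation | 0.0% | 0.2% | 1.7% | 2.8% |

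Confirmation alone leaves the error high at 1 to 2% blasts. The floor alone leaves 11% at a true 4% and 15% at a true 5%, because a baseline that is high by chance passes it. Together they leave about 2 to 3% at 4 to 5%. A patient at a true 4% who does pass the floor by chance (18% of such patients) still has a 0.028/0.180 = 16% chance of a confirmed false marrow CR, so the residual is small overall but not zero.

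**The case against.** The strongest reply is that the duration requirement already covers this. With marrows 8 weeks apart, the natural way to show 4 weeks is that the next marrow still qualifies, so the two-consecutive rows are the relevant ones. That stands in part. Those rows are much lower than best of three, and at 3 to 4% blasts with 500 cells little is left. But the plan does not state this reading, and even under it the 200-cell figures at 1 and 2% blasts are 25% and 12%.

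A reader might infer that about half or more of stable low-blast patients would be scored complete remissions, from best-of-three figures such as 68% and 47%. The documents do not support that. It sets the duration rule aside, assumes that refractory or intolerant patients stay through cycle 6, and takes the lowest blast levels with 200 cells. The events would be CRi, which the plan also lists separately from CR.

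The rule is also the cited 2006 IWG table, and changing it costs comparability. That stands, and is why the unmodified rate should still be reported. It does not remove the problem: the plan itself combines that table with unrestricted entry blasts and a pooled complete remission rate.

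Finally, response is secondary, no hypothesis test or response-based go/no-go rule depends on it, and a full SAP is still to be finalised before database lock. All true; this limits the weight of the point but not its correctness.

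**Conclusion.** The point holds. Applied as written, the rule can score a change from 2% to 1% as marrow CR, hence CRi, hence a complete remission in the pooled rate and a response in ORR. The risk is material mainly at 1 to 2% blasts or with about 200 cells counted. It is small at 4% blasts with 500 cells: 1% on one marrow and 3% as best of three.

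The conclusion rests on these limits:

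- The cell count is assumed.
- The documents give no baseline blast distribution, so the number of affected patients is unknown and could be zero.
- Extension to CMML is an inference. Sections 7.2.1 and 13.4.2 send it to Appendices I and II, but 3.2.2 names criteria only for acute leukemia and MDS.
- The marrow CR row carries a footnote mark whose text is not in the available copy, so a qualifier there could not be checked.

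A reader might also infer that the trial's main conclusion is threatened. It is not: safety and the MTD do not depend on response.

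**What to change.** Amend 3.2.2, 13.2.1 and Appendix II, and carry the wording into the full SAP:

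- For the pooled remission rates, count marrow CR as CRi only if baseline marrow blasts exceed 5% and the criterion is still met on the next scheduled marrow. State that this is how the 4-week duration is shown.
- Report a marrow CR without a later marrow, including one first seen at the end of cycle 6, as unconfirmed and outside the pooled rate.
- Keep patients with 5% or less at baseline in the denominator; they can still respond by full CR.
- List the baseline blast percentage beside each marrow CR.
- Report the rate under the unmodified 2006 IWG rule as a sensitivity analysis.
- State whether Appendix II applies to CMML.

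The cost is wording and analysis only. The baseline count is already recorded and the later marrows are already scheduled, so none is added; the discretionary wording in footnote 3 of 8.1 should be reconciled with footnote 4 of 8.2. The headline rate may be slightly lower and departs from the cited criteria, which the sensitivity analysis covers.

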Appendix III – ECOG Performance Status

ECOG Score	Performance Status
0	Asymptomatic
1	Symptomatic, fully ambulatory
2	Symptomatic, in bed < 50% of the day
3	Symptomatic, in bed > 50% of the day but not bedridden
4	Bedridden
5	Dead

Appendix IV – New York Heart Association Classification

Class	Functional Capacity	Objective Assessment
I	Patients with cardiac disease but without resulting limitations of physical activity. Ordinary physical activity does not cause undue fatigue, palpitation, dyspnea, or anginal pain.	No objective evidence of cardiovascular disease.
II	Patients with cardiac disease resulting in slight limitation of physical activity. They are comfortable at rest. Ordinary physical activity results in fatigue, palpitation, dyspnea, or anginal pain.	Objective evidence of minimal cardiovascular disease.
III	Patients with cardiac disease resulting in marked limitation of physical activity. They are comfortable at rest. Less than ordinary activity causes fatigue, palpitation, dyspnea, or anginal pain.	Objective evidence of moderately severe cardiovascular disease.
IV	Patients with cardiac disease resulting in inability to carry on any physical activity without discomfort. Symptoms of heart failure or the anginal syndrome may be present even at rest. If any physical activity is undertaken, discomfort is increased.	Objective evidence of severe cardiovascular disease.

Appendix V – Prohibited Concomitant Medications

Mercaptopurine
Concomitant other anti-cancer therapy (cytotoxic, biologic, or radiation)

Appendix VI – Medications to use with caution, see Sections 7.4 and 7.6

NSAIDs
Phenytoin
BACTRIM (trimethoprim/sulfamethoxazole)
Sulfonamides
Phenylbutazone
Salicylates
Oral antibiotics
Penicillins
Azathioprine
Retinoids
Sulfasalazine
other potential hepatotoxins
Theophylline
Folic acid vitamin supplement
